5.1 Design

Single center, prospective observational study. No intervention groups, one single cohort.

5.2 Number of Project Participants

We aim to include at least 500 up to 2200 patients. For further informations see below.

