Inclusion criteria:	
 • All elective in-hospital Rapid Sequence Inductions (RSI) and patients with one or more aspiration risk factors scheduled for a advanced laryngeal mask or regional anaesthesia with informed consent. • All emergency in-hospital RSI and patients with one or more aspiration risk factors scheduled for an advanced laryngeal mask or regional anaesthesia with informed consent graded as follows according to the Swiss Society for Anaesthesiology and Resuscitation (A-QUA): “Notfall 1-6h, nicht vital (dringlicher Eingriff)”, “Notfall 6-24h nicht vital (aufgeschobener dringlicher Eingriff)”
Exclusion criteria:	
 • Life threatening/ time critical emergency interventions, graded followingly according to the Swiss Society for Anaesthesiology and Resuscitation (A-QUA): “Notfall <1h, vital (sofortiger Eingriff notwendig)” • Known Pregnancy • Obstetric surgery • Underage (< 18 years) • Absence of informed consent (missing or inability to provide) • No anaesthetist with completed structural education in gastric sonography is available. • Contraindications for naso- or orogastric tubes or inability to correctly place such.
Intervention, Measurements and procedures:	Our study will be performed mainly in the induction rooms of our operating ward and occasionally inside the operating theatre. Standard care will be given to every patient at the usual location, with our usual equipment (anaesthetic machine, monitoring, medication and airway devices etc) and by our usual anaesthesiologic team members. Sonographic examination and determination of the gastric content will be executed on one of our standard ultrasound machines (Venue and LOQIC e from GE-Healthcare®) with a curved

	array low frequency (2-10 Hz) abdominal probe or portable ultrasound devices (IQ+ from Butterfly Network Inc. ®).
Control Intervention:	
Number of Participants with Rationale:	A total number of 2'718 general anaesthesia with Rapid Sequence Inductions (RSI) was undertaken at our institution in 2019. Thereof, 275 were children < 18 years of age. 204 Rapid Sequence Inductions were performed in category: "Notfall <1h, vital, sofortiger Eingriff notwendig" and therefore not includable. Therefore, expect to include around 1500 - 2200 patients in a one year period.
Study Duration:	Estimated duration of the project: 18 months Planned start: 01/2021 Planned project close: 06/2022

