Within a study period of 6 to 12 months, all elective and emergency patients with one or more risk factors for pulmonary aspiration will be screened for possible participation in this study. The risk factors for pulmonary aspiration are previously determined by the responsible anaesthetist and based on patient medical history and clinical findings according to department standards. With the given information and in line with department policy, the responsible anaesthesiologist will predefine an individual management for the patient, in form of an advanced laryngeal mask, a RSI or a regional anaesthesia. No changes in or adaptations of the established clinical practice will be made for the sole purpose of this study.

The responsible anaesthesiologist will work through the list of inclusion and exclusion criteria. Of note, patients which are of the highest urgency where a delay is medically and ethically not acceptable, will not be included in this study. Also, patients where ability to consent is not given due to patient or circumstantial reasons, will be excluded.

Thereafter, further recruitment and informed consent will be obtained during a regular anaesthesia specific discussion, which can take place on the ward, in our preoperative consultation for elective surgery or the emergency department. If a patient qualifies for this study according to our inclusion criteria, a qualified study person will explain the nature of the study to each participant, its purpose, the procedures involved, the expected duration, the potential risks and benefits and any discomfort it may entail, according to good clinical practice guidelines. Members of the department of anaesthesia will receive a training by the PI and investigators prior to appointment as qualified study person with delegated informed consent authorization. Each participant will be informed that the participation in the study is voluntary and that he/she may withdraw from the study at any time and that withdrawal of consent will not affect his/her subsequent medical assistance and treatment.

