11.1 Determination of Sample Size

Within a study period of 6 to 12 months, all elective and emergency patients scheduled for a Rapid Sequence Induction (RSI) will be included in this study. In 2019, a total of 2'718 general anaesthesias with Rapid Sequence Inductions (RSI) were undertaken at our institution. 275 thereof were children < 18 years of age. Further, 204 Rapid Sequence Inductions were performed in life threatening situations (category: Notfall <1h, vital, sofortiger Eingriff notwendig by the Swiss Society for Anaesthesiology and Resuscitation, A-QUA) where a delay is medically and ethically not acceptable. Further, we estimate that a number of 1000 patients per annum have one or more aspiration risk factors, receiving an advanced laryngeal mask or a regional anaesthesia. In conclusion, we aim to include at least 1500 up to 3200 patients in a one year recruitment period. On basis of the publication of Arzola et al.³⁶ individual differences in sonography performance can already be detected after 30 to 40 examinations. Although our residents will already have performed at least as many examinations before first patient inclusion, we postulate, that a similar number of patients per capita will be needed to investigate interindividual performance. Given an estimated number of 30 residents and 20 attendings participating, we aim to include 1500 - 2000 patients.

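### Section 5.2's minimum of 500 patients has no stated basis and contradicts the 1500 in section 11.1; the upper limits 2200 and 3200 are yearly patient pools worded as aims

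*Protocol*

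**What the plan says.** The protocol gives four enrolment ranges.

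- **Section 5.2:** "We aim to include at least 500 up to 2200 patients", with a pointer to later text.
- **Synopsis (number of participants):** "Therefore, expect to include around 1500 - 2200 patients in a one year period". This is a forecast, and the counts listed before it are all RSI counts.
- **Section 11.1, availability:** "In conclusion, we aim to include at least 1500 up to 3200 patients in a one year recruitment period". This follows the RSI counts and the statement that "we estimate that a number of 1000 patients per annum have one or more aspiration risk factors", meaning patients who receive an advanced laryngeal mask or regional anaesthesia.
- **Section 11.1, requirement:** "Given an estimated number of 30 residents and 20 attendings participating, we aim to include 1500 - 2000 patients". The basis is a cited learning-curve study in which individual differences show after 30 to 40 examinations, and "we postulate, that a similar number of patients per capita will be needed to investigate interindividual performance".

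The opening sentence of 11.1 says that "all elective and emergency patients scheduled for a Rapid Sequence Induction (RSI) will be included in this study". The inclusion criteria in 7.1 also admit mask and regional patients with an aspiration risk factor, and later sentences of 11.1 count them.

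On timing, the synopsis and 5.3 give 12 months of recruitment. Section 7 and the start of 11.1 say "Within a study period of 6 to 12 months".

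**The concern.** Section 5.2 is where a reader looks for the number of participants. Its lower limit is a third of the one in the sample-size section, and the onward pointer leads to text that does not explain it. Both 5.2 and 11.1 use minimum wording, so the protocol holds two conflicting floors.

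What is at stake is the analysis of individual performance: the critical number of examinations, residents against attendings, and the logistic regression and cumulative sum learning curves in 11.2. These depend on how many examinations each sonographer performs. If recruitment were slow, a study of 500 could be reported as having met its stated aim while falling well short of the count that 11.1 says it needs.

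The upper limits are a second, smaller problem. If 2200 and 3200 count the patients available in a year, they say nothing about what the analysis needs and should not be worded as aims.

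**Working it through.** **Inputs.** From 11.1: 30 residents and 20 attendings; 30 to 40 examinations each; 2718 RSIs in 2019, of which 275 in children and 204 in the immediate-emergency category; 1000 mask or regional patients a year. From the synopsis and section 6: 25 staff and 29 trainee anaesthetists.

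**1. The derived target reproduces.**
- Sonographers: 30 + 20 = 50.
- Lower end: 50 x 30 = 1500. Upper end: 50 x 40 = 2000.

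**2. Average examinations per sonographer (total / 50).**

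| Total | Per sonographer |
|---|---|
| 500 | 10 |
| 1500 | 30 |
| 2000 | 40 |
| 2200 | 44 |
| 3200 | 64 |

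At 500 the average is 10/40 = 25% to 10/30 = 33% of the stated need. No combination of inputs given in the protocol yields 500.

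**3. The upper limits reproduce as yearly pools.**
- RSI only, if no child was also an immediate emergency: 2718 - 275 - 204 = 2239, about 2200.
- With mask and regional patients: 2239 + 1000 = 3239, about 3200.
- Share of the pool needed: 2200/2239 = 98%; 3200/3239 = 99%.
- If all 204 immediate emergencies were among the 275 children: 2718 - 275 = 2443, and 2443 + 1000 = 3443. The shares become 2200/2443 = 90% and 3200/3443 = 93%.

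All these pools are before losses for missing consent, pregnancy, obstetric surgery or tube contraindication. By contrast, 1500 to 2000 is 1500/3239 = 46% to 2000/3239 = 62% of the full yearly pool.

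**4. Recruitment period, assuming even accrual over the year.**
- Six-month full pool: 3239/2 = 1619.5, about 1620.
- 1500/1619.5 = 93%; 2000/1619.5 = 123%.
- With full overlap of the two exclusions: 3443/2 = 1721.5, giving 87% and 116%.

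Six months could therefore only just supply 1500 and could not supply 2000.

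**5. Sonographer count.** Section 6 gives 25 + 29 = 54 physicians. The same rule then gives 54 x 30 = 1620 to 54 x 40 = 2160. Fewer participating attendings than staff (20 of 25) is easy to understand, but 30 residents exceeds the 29 trainees listed.

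**The case against.** The strongest reply is that the protocol already answers the question. Section 5.2 points onward, and 11.1 holds the derivation and ends on 1500 to 2000. The 500 may be a slip for 1500. The intended target can indeed be recovered, but nothing in the document shows that 500 is a slip, and a wrong floor in the participant-number section still needs correcting.

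Other parts of the reply stand and limit the point:

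- A reader might infer that the four ranges are mutually incompatible. They are not. Any enrolment from 1500 to 2000 lies within all four, one of which is the derived target itself. The conflict is over the limits.
- A reader might infer that 1500 is the stated minimum everywhere else. Only one other sentence, in 11.1, words it as a minimum. The synopsis gives a forecast, and the last sentence of 11.1 gives a range.
- A reader might infer that the wording on the study period makes the target infeasible. Twelve months lies within it, and six months could still just yield 1500. The lower figure of about 1120 patients in six months (2239/2) needs an RSI-only reading, which the rest of 11.1 and the inclusion criteria contradict.
- A reader might infer that the study would stop at 500 or that the primary endpoint is undermined. No rule stops it at 500, and the primary correlation pools all examinations, so it does not depend on the count per sonographer.
- Ten per sonographer is an average that assumes equal sharing. With uneven sharing, 500 patients could give 500/40 = 12.5 to 500/30 = 16.7, so about 12 to 16, sonographers their 30 to 40 examinations. That is still far from 50.

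**Conclusion.** The point holds as an internal inconsistency that should be fixed. It is not an arithmetic error, since the derived target reproduces exactly and both upper limits closely.

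The floor in 5.2 is unsupported and contradicts 11.1. On average it supplies a quarter to a third of the examinations per sonographer that the protocol postulates for its interindividual analysis. The consequence is confined to secondary endpoints.

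The limits 2200 and 3200 are availability figures worded as aims in 5.2 and 11.1. The 2200 leaves out the mask and regional patients whom the inclusion criteria admit. For the synopsis this is plain from the counts listed. For 5.2, which shows no working, it is inferred from the match with 2239.

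The conclusion on the floor rests on 50 sonographers and roughly equal sharing. The pool figures rest on 2019 volumes and, for 2239 and 3239, on no overlap between the two exclusions. Full overlap does not change the reading. The recruitment-period wording is a minor note.

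**What to change.** - **Section 5.2:** replace the 500 to 2200 range with the 1500 to 2000 derived in 11.1. If 500 is kept as a floor, state that it does not support the individual-performance analysis.
- **Synopsis and 11.1:** label 2200 and 3200 as patients available in a year, and say that the first counts RSI patients only and the second adds mask and regional patients.
- **11.1, opening sentence:** make the population match the inclusion criteria in 7.1.
- **11.1, target:** confirm the number of participating sonographers against the staffing in the synopsis and section 6 before restating the target, since 54 would give 1620 to 2160.
- **Section 7 and 11.1, wording note:** give the recruitment period as 12 months, as in the synopsis and 5.3. Section 5.3 needs no change.

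The cost is protocol wording in the synopsis and sections 5.2, 7 and 11.1. Procedures, endpoints and analyses are unchanged, and no extra patients are needed beyond the target that 11.1 already derives, unless the sponsor confirms a different sonographer count.

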5.3 Project Schedule

Estimated duration of the project:	18 months
Time period for participant recruitment:	12 months
Project start (FPFV):	01/2021
Project end (LPLV):	12/2021

5.4 Risk-benefit considerations

Gastric sonography is as an accurately investigated and validated tool to assess a patients fasting status and thus probably aspiration risk. Some authors recently highlighted its possible impact on anaesthesiologic management in finding an appropriate technique for individual patients and thus balance risks and benefits. Nevertheless, gastric sonography has not yet found its role in clinical practice. This prospective observational-study with its large sample size and thorough analysis may help to identify crucial determinants and possible obstacals in establishing gastric sonography in daily practice and may thus contribute to patient safety. Further, participating medical staff benefit from a structured education in performing this examination with high precision and quality.

With this study being observational, non interventional, all patients receive the standard of care in form of a predefined, independent anaesthesiologic treatment and do not carry additional risks besides possible side effects due to gastric sonography itself, which are minimal. The possible delay in the anaesthesiologic management ist at maximum a few minutes and patients with time critical interventions will be thoroughly excluded. In exceptional cases the responsible anaesthesiologist is allowed to upgrade patients from an advanced laryngeal mask to a RSI (gold standard) after ultrasound performance to ensure patient safety. Downgrading from RSI to advanced laryngeal maks on base of the ultrasound results is not allowed.

6 Eligibility of the Project Site

This study will be conducted at the Department of Anaesthesiology at the Cantonal Hospital of Winterthur, a Swiss teaching hospital. In our department we care for a total of approximately 18'000 patients a year. The anaesthesiologic physician team consists of 25 qualified/staff anaesthetists and 29 trainee anaesthetists. In the past several clinical studies including multi- as well as single-center studies have been successfully conducted at our institution. Commulative experience of the assigned staff are high: They have participated in several observational studies as well as interventional studies and Phase III trials. An experienced study coordination team is available at site and involved in coordination and planning.

7 Recruitment

Within a study period of 6 to 12 months, all elective and emergency patients with one or more risk factors for pulmonary aspiration will be screened for possible participation in this study. The risk factors for pulmonary aspiration are previously determined by the responsible anaesthetist and based on patient medical history and clinical findings according to department standards. With the given information and in line with department policy, the responsible anaesthesiologist will predefine an individual management for the patient, in form of an advanced laryngeal mask, a RSI or a regional anaesthesia. No changes in or adaptations of the established clinical practice will be made for the sole purpose of this study.

The responsible anaesthesiologist will work through the list of inclusion and exclusion criteria. Of note, patients which are of the highest urgency where a delay is medically and ethically not acceptable, will not be included in this study. Also, patients where ability to consent is not given due to patient or circumstantial reasons, will be excluded.

Thereafter, further recruitment and informed consent will be obtained during a regular anaesthesia specific discussion, which can take place on the ward, in our preoperative consultation for elective surgery or the emergency department. If a patient qualifies for this study according to our inclusion criteria, a qualified study person will explain the nature of the study to each participant, its purpose, the procedures involved, the expected duration, the potential risks and benefits and any discomfort it may entail, according to good clinical practice guidelines. Members of the department of anaesthesia will receive a training by the PI and investigators prior to appointment as qualified study person with delegated informed consent authorization. Each participant will be informed that the participation in the study is voluntary and that he/she may withdraw from the study at any time and that withdrawal of consent will not affect his/her subsequent medical assistance and treatment.

After the discussion, an additional information brochure and consent form will be handed to all possible participants providing sufficient information to make an informed decision. The patient will be asked to carefully read and review the form, clarify possible questions at any time and sufficient time will be provided before signing. After the participants signature, the form will also be dated and signed by the study person and retained as part of the study records. If the patient needs further time for consideration the patient may sign the informed consent together with the responsible anaesthetist on the day of surgery, after a overnight reflection period. If unanswered questions arise or the patient need further clarifications a special appointment with a physician of the study team is available anytime. The participant will receive a copy of the signed informed consent.

The participant will be informed that his/her medical records may be examined by authorised individuals other than their treating physician.

7.1 Inclusion Criteria

Subjects, who will fulfil all the following inclusion criteria, may be included into this project:

- All elective in-hospital Rapid Sequence Inductions (RSI) and patients with one or more aspiration risk factors scheduled for an advanced laryngeal mask or regional anaesthesia with informed consent.

- All emergency in-hospital RSI and patients with one or more aspiration risk factors scheduled for an advanced laryngeal mask or regional anaesthesia with informed consent graded as follows according to the Swiss Society for Anaesthesiology and Resuscitation (A-QUA): “Notfall 1-6h, nicht vital (dringlicher Eingriff)”, “Notfall 6-24h nicht vital (aufgeschobener dringlicher Eingriff)”

7.2 Exclusion Criteria

If a subject fulfils any of the following exclusion criteria he/she may not be included:

- Life threatening/ time critical emergency interventions, graded followingly according to the Swiss Society for Anaesthesiology and Resuscitation (A-QUA): Notfall <1h, vital (sofortiger Eingriff notwendig)
- Known pregnancy
- Obstetric surgery
- Underage (< 18 years)
- Absence of informed consent (missing or inability to provide)
- No anaesthetist with completed structural education is available.
- Contraindications for naso- or orogastric tubes or inability to correctly place such.

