Fast, simple, non-invasive and cost-effective strategies to assess a patient's risk of aspiration and adapt the anaesthetic strategy accordingly are greatly needed. Here, point-of-care sonography (POCUS) with preoperative assessment of the gastric content allows a fundamentally new approach for patients at risk of gastric regurgitation by adding an objective tool - not relying on patient history alone.^{11, 20} Gastric sonography seems to be highly sensitive and specific.^{21, 22} Recent studies, especially highlighted the accuracy for the qualitative²³⁻²⁷ and quantitative assessment^{22, 25, 26, 28} of the gastric content. For the quantitative analysis of gastric content, present data suggest a strong numerical correlation between an ultrasound-determined antral cross-sectional area (CSA) and the total volume of gastric fluid.^{11, 28} A residual gastric volume of more than 1.5 ml/kg for fluid content has been identified to signal an increased risk for gastrointestinal regurgitation and for pulmonary aspiration and this cut-off value has been utilized in various studies.^{20, 29} Consequently, there is an increasing consensus in scientific literature that preoperative gastric sonography should be performed in all emergency situations and in elective interventions in patients with increased probability of presenting with a full stomach and accordingly an increased risk of pulmonary aspiration.³⁰⁻³⁴ The routine application of gastric POCUS for elective surgery with fasted patients without risk factors is still controversial¹¹ although Van de Putte et al.³⁵ discovered a relevant percentage of full-stomachs in patients without risk factors of delayed emptying of the stomach.

In summary, preoperative gastric sonography may provide a validated, reliable, fast, and cost-efficient approach to assess aspiration risks in both elective and emergency patients. Practiced sonographers are able to perform point-of-care gastric sonography in few minutes^{11, 27}, thus severe delay in daily clinical practice should not be expected. Nevertheless, how this highly sensitive and specific tool should be best established in daily clinical practice is further on unclear. There is no existing structural education/training for this specific point-of-care ultrasound application. Arzola et al. suggest a minimum of 30 ultrasounds an acceptable quality level, but evidence is scarce.³⁶

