7.3 Premature Withdrawal Criteria

Premature withdrawal of a participant:

- Participants may withdrawal their informed consent at anytime. If gastric sonography has already been performed, anonymous analysis of the previously collected data is eligible.
- Discomfort or pain experienced by the patient at any time of the sonography.
- In case of inability to safely perform the sonography within a maximum of 10 minutes, futher attempts will be stopped and the patient excluded.
- Arising medical or personal information at any time, increasing the urgency of the intervention.

Premature termination of the project:

As this study is designed in a observational, non-interventional methodology, and all patients receive the standard of treatment , no premature termination should occur.

8 Project Measures

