8.1 Measures/procedures to collect health related personal data

At Kantospital Winterthur, a mid-size Swiss teaching hospital all residents and attending anaesthesiologists will receive a structured training in a period of 1 to 8 weeks before inclusion of the first patient. All participating staff will give written informed consent to participate in the study.

To achieve a 90% success rate in correctly recognizing gastric content quality in healthy volunteers, Arzola et al.³⁶ postulated an average number of 24 sonographic examinations to be performed. Based on this and further scientific studies we designed a structured training for all residents and fellows. Primarily, at least 120 minutes of self-study is mandatory for all participants, consisting of scientific background literature, a step for step guide and educational videos. This is followed by a hands-on course, split into a 30 minute lecture and theoretic background introduction and 120 minutes supervised practical training on healthy volunteers. Group sizes per ultrasound machine and tutor/expert will range from 2 to 3 participants. First training objective is a successful differentiation of gastric content into empty, fluid, solid or mixed. An empty stomach seems the hardest quality to sonographically visualise,³⁶ therefore a special effort will be made on identifying this quality. The next objective is the identification and localization of the antral cross-sectional area in a supine and right lateral decubitus (RLD) position in the case that fluid gastric content is present. Every participant will perform at least 20 examinations during this hands-on course with a direct expert feedback.

Further, all participants will continue to train their sonographic skills on healthy volunteers and team members at our institution. Before including the first patient all the examiners will be tested by a tutor/expert and received their approval. In the first month of recruitment, new sonographers will be supervised by our tutor/expert team whenever possible. Individual feedback and support if needed should be available any time.

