Tutors/experts are all expert sonographers on different modalities. They will receive a preceding 240 minutes training, consisting of a 60 minutes theoretic introduction and a 60 minutes course by a radiologist and abdominal sonography expert, certified by the Swiss Society for Sonography. The remaining time will consist of individual exercise on healthy volunteers and at least 10 trial sonographies with gastric volume calculation under supervision of another member of the tutor group.

Our study will be performed mainly in the induction rooms of our operating unit and occasionally inside the operating theatre. Standard care will be given to every patient at the usual location, with our usual equipment (anaesthetic machine, monitoring, medication and airway devices and so on) and by our usual anaesthesiologic team members. Sonographic examination and determination of the gastric content will be executed on one of our standard ultrasound machines (Venue and LOQIC e from GE-Healthcare®) with a curved array low frequency (2-10 Hz) abdominal probe or our portable ultrasound devices (IQ+ from Butterfly Network Inc.®).

Before performing the sonographic examination, the responsible anaesthesiologist will be asked to rate the estimated risk of pulmonary aspiration, based on personal impression, patient history and clinical finding. All anaesthetists are advised to perform the examination only if they could guarantee privacy before they expose patient abdomen for the examination. Primarily, a qualitative assessment of the gastric content should be performed in supine and right-lateral decubitus (RLD) position. In low volume states a right-lateral decubitus position (RLD) has the advantage of a gravitational shift to the antrum. That is why we plan to perform the examination in both positions. If RLD position is not possible due to patient factors a half sitting position can be tried. Gastric content will be classified into empty, fluid, solid or mixed. Examiners will be asked to classify sonographic conditions into poor, medium or good and provide a reason in case of limited conditions. If fluid gastric content is detected an estimation of the quantity should be performed as follows.

After identification, CSA will be measured and gastric content is estimated by implementation of the formula described by Perlas et al: ^{20, 28}

$$\text{Gastric Volume (ml)} = 27.0 + 14.6 \times \text{right-lateral CSA (cm}^2\text{)} - 1.28 \times \text{age (years)}.$$

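### Nothing keeps patients with surgically altered gastric anatomy out of the volume comparison, although volume is always computed from an antral cross-section with one fixed equation

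*Protocol*

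**What the plan says.** **Who enters.** Protocol section 7.1 admits "All elective in-hospital Rapid Sequence Inductions (RSI) and patients with one or more aspiration risk factors" scheduled for a laryngeal mask or regional anaesthesia, and the same groups in two non-vital emergency grades. It sets no anatomical limit.

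**Who is kept out.** Section 7.2 begins "If a subject fulfils any of the following exclusion criteria he/she may not be included". Its seven items are vital emergencies, known pregnancy, obstetric surgery, age under 18, absent consent, no trained anaesthetist available, and "Contraindications for naso- or orogastric tubes or inability to correctly place such". The synopsis list is the same in substance. Section 7.3 adds withdrawal, among other reasons, "In case of inability to safely perform the sonography within a maximum of 10 minutes".

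**How volume is obtained.** Section 8.1 states: "After identification, CSA will be measured and gastric content is estimated by implementation of the formula described by" a cited validation study, namely volume (ml) = 27.0 + 14.6 × right-lateral CSA (cm²) − 1.28 × age (years). This is done when fluid content is found. Section 3.1 describes the relation as one between an "ultrasound-determined antral cross-sectional area (CSA) and the total volume of gastric fluid", and the training in 8.1 aims at "identification and localization of the antral cross-sectional area in a supine and right lateral decubitus (RLD) position". No other equation is given.

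**How it is used.** Section 8.1 compares calculated with suctioned volume to judge the sonographic measurement. Their correlation is the primary endpoint (4.2, 11.2). Agreement above 80% in fluids is the quality standard for the learning question (4.2), and 11.2 plans logistic regression and cumulative sum curves by examiner.

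**The concern.** The equation takes one anatomical input, the area of the antrum. After gastric resection, bypass or sleeve surgery, the antrum may be missing, cut off from the part that holds the fluid, or changed in shape. An examiner who measures a fluid-filled cross-section in such a patient puts into the equation something other than what it was built on. The tube may also drain a different compartment from the one scanned.

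The two volumes can then disagree however well the scan was done. The plan would count that disagreement against the training programme in the primary comparison, and against whichever examiner happened to scan the patient. Section 4.1 makes identifying confounders in individual training a secondary objective; this is one that can be named beforehand.

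**Working it through.** **1. The plan's own number.** Section 11.1 expects 30 residents and 20 attendings, with 30 to 40 examinations each: 50 × 30 = 1500 and 50 × 40 = 2000. The stated 1500-2000 reproduces.

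**2. Which rules could remove an operated stomach.**

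| Rule | Section | Acts when |
|---|---|---|
| Tube criterion | 7.2, 8.1 | a tube is contraindicated or cannot be placed correctly |
| Identification step | 8.1 | the examiner cannot identify the structure, so no CSA is measured |
| 10-minute rule | 7.3 | the scan cannot be done safely in time |

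Each may remove some of these patients. None is tied to anatomy. If a tube passes and a cross-section is measured in time, the patient enters the comparison.

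**3. How many comparisons.** Only patients with fluid content and a tube contribute; 8.1 gives regional anaesthesia patients no tube. Neither share below is in the protocol. Both are assumptions, and the share with altered anatomy is taken as the same inside and outside the compared subset.

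- Altered anatomy: 1-5%.
- Fluid content and a tube: 30-50%.
- N = 1500, low end: 1500 × 0.01 × 0.30 = 4.5, about 5. High end: 1500 × 0.05 × 0.50 = 37.5, about 38.
- Per examiner: 4.5 / 50 = 0.09 to 37.5 / 50 = 0.75.
- N = 2000: 6 to 50 comparisons, or 0.12 to 1.0 per examiner.

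These counts are before the rules in step 2 remove anyone.

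**4. Effect on the pooled correlation.** Suppose a share q of the compared patients has a CSA unrelated to volume, with the same means and variances as the rest. The covariance shrinks by the factor (1 − q), so r = (1 − q) × r0. The values of r0 are illustrative.

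| r0 | q = 1% | q = 2% | q = 5% |
|---|---|---|---|
| 0.80 | 0.792 | 0.784 | 0.760 |
| 0.90 | 0.891 | 0.882 | 0.855 |

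Simulation agrees to within 0.001. In a harsher case, where all these patients also have an aspirate 1.5 SD below the mean, q = 5% gives 0.739 and 0.832.

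**5. Effect on one examiner.** Read the standard as more than 80% of an examiner's volume comparisons in agreement (a reading; 4.2 does not define congruence further). With 30 scans each and 30-50% usable, an examiner has 9 to 15 comparisons.

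- 9 comparisons: more than 7.2 must agree, so 8; one miss is allowed.
- 12 comparisons: more than 9.6, so 10; two misses.
- 15 comparisons: more than 12, so 13; two misses.

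One patient outside the formula's reach can therefore use half or all of the allowance. If cases fall independently, the chance that an examiner draws at least one runs from 1 − 0.99⁹ = 0.09 to 1 − 0.95¹⁵ = 0.54.

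**The case against.** The strongest reply is that the key premise is not in the protocol. It speaks of an antral area and a right-lateral CSA; it does not describe the population in which the equation was validated or say where it stops applying. That is correct. The step from an operated stomach to an unusable input is anatomical reasoning and should be presented as such.

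Second, existing rules already catch some of these patients. Also correct: the point is that none is aimed at anatomy, not that all such patients pass through.

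Third, analysis populations are often left to a statistical analysis plan, which is not shown here, and broad enrolment suits a study of daily practice. This stands in part. A separate plan could set these patients aside, and the history needed is already collected. But eligibility and the single volume equation are fixed in this protocol, and as written they let these patients into the comparison.

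A reader might also infer more than the text allows:

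- **That 15-75 scans are affected** (1-5% of 1500). This ignores that only fluid-content patients with a tube are compared.
- **That such patients concentrate in this cohort.** The risk factors listed in 3.1 do not name previous gastric surgery; enrichment is conjecture.
- **That 14.6 ml per cm² measures the error.** It is only the equation's slope and says nothing about the error in these patients.

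**Conclusion.** The gap is real but small: neither the eligibility criteria nor the measurement section sets apart patients whose antrum surgery has altered, while one antral equation serves every fluid stomach. On the assumed shares, about 5-38 of the comparisons from 1500 patients are affected, and an illustrative correlation of 0.80 would move to about 0.79-0.76. The consequence lies mainly in individual learning curves, where few comparisons per examiner make a single inapplicable case count.

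It would be tempting to conclude that the primary result is invalid or that the study tests the formula more than the training. Neither follows: the pooled effect is modest unless such patients are common, and the documents give no prevalence. No stated figure is wrong. This is an optional, inexpensive improvement.

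**What to change.** State in advance, in 7.2 or 8.1 or in the definition of the population for the volume comparison, that patients with previous gastric surgery altering the antrum or its continuity with the gastric body are left out of the comparison of estimated with aspirated volume and out of the volume-based examiner performance analysis. Identify them from the patient history recorded before the scan, so that nobody is removed because the two volumes disagreed. Keep them in the endpoints that need no volume: content class, examination time and aspirations. Report how many were set aside.

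The cost is one sentence and no new data. Slightly fewer scans are compared, and the volume conclusion is limited to unaltered gastric anatomy.
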